**Recording and Reporting:**

The Investigator records each AE occurring in the study, including those not thought to be associated with the drug, on the Adverse Event Record. Documentation includes the AE description, severity at onset, seriousness, date of onset and resolution, relationship to the investigational drug, action taken, and outcomes.

The Investigator must promptly report all adverse drug experiences to the 3M study monitor. If the adverse drug experience is also considered by the Investigator to be serious and/or unexpected the Investigator must report it to the IRB/EC as soon as possible.

3M reports (by telephone or fax) a death or life-threatening adverse drug experience to the FDA within 7 days of notification, and submits a follow-up report within 15 days.

A serious and unexpected adverse drug experience involving a non-3M commercialized product is reported to the 3M study monitor and IRB/EC.

If a subject does not experience an AE during the study, the absence of such must be recorded on the form.

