### **3.5 Study Duration**

The expected duration of this study for each subject is up to 3 weeks. Each subject's participation will involve at least a 14-day Wash Out (Pre-inclusion) Phase, a 1-day Screening Phase, and a 1-day Treatment Phase. Following the Wash Out (Pre-inclusion) Phase, each subject will be required to visit the test facility on an arranged date for collection of screening baseline samples from the back region. Subjects will remain on washout until notified that they do or do not qualify for the study. Subjects whose screening baseline samples meet the requirements described in the inclusion criteria (Section 4.1) will be notified and invited to participate in the Treatment Phase of the study. The Treatment Phase will be scheduled no sooner than 72 hours from the screening baseline collections. Each subject who chooses to participate in this study will be required to return to the test facility for treatment and sample collection. Table 3.1A indicates the sequence of events throughout the study and a schematic diagram of the study is included in Appendix 14.1.

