## **4. SUBJECT SELECTION**

Healthy male subjects will be recruited. A suitable number of subjects will be enrolled in the wash out (pre-inclusion), screening and treatment phase, such that a total of 18 subjects are evaluable for efficacy at completion of the study.

[REDACTED]

Subjects must follow all Subject Instructions (Appendix 14.5) and satisfy inclusion/exclusion criteria prior to enrollment into the treatment phase of the study.

All subjects will be provided verbal and written information about the study procedures, and subject instructions (Appendix 14.5). The following inclusion/exclusion criteria will be reviewed on wash out (pre-inclusion), screening and treatment day to establish eligibility for participation:

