## **7. ASSESSMENT OF SAFETY**

### **7.1 Safety Parameters**

The principal measure of safety will be the incidence of adverse events reported during the study and a summary of the skin irritation rating scores. [REDACTED]

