**Definitions:**

- Adverse event (AE) means any undesirable clinical occurrence in a subject whether or not it is considered to be drug related.
- Drug-related adverse event (ie, adverse drug experience) is an adverse event that is considered by the Investigator to have a reasonable likelihood of being associated with the investigational drug.
- Life-threatening adverse drug experience is any adverse drug experience that places the subject, in the view of the Investigator, at immediate risk of death from the reaction as it occurred (does not include a reaction that, had it occurred in a more severe form, might have caused death).
- Serious adverse drug experience is an adverse drug experience that is fatal or life-threatening, is permanently or significantly disabling/incapacitating, requires inpatient hospitalization or prolongation of existing hospitalization, or results in a congenital anomaly/birth defect.
- Unexpected adverse drug experience is one not previously identified in nature, severity or frequency of incidence in the current Investigator brochure, in the clinical plan, or elsewhere in the current IND application and amendments.

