### 8.2.2 Safety Analyses

Adverse events, [REDACTED] will be summarized.

Skin irritation tables will be produced at baseline collection and post-prep sample collection.

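### The only severity item named for the adverse event record is severity at onset, so an event that later worsens without becoming serious need not be re-graded

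*Combined protocol and SAP*

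**What the plan says.** Section 7.3 (Recording and Reporting) gives the contents of the adverse event record as "Documentation includes the AE description, severity at onset, seriousness, date of onset and resolution", and then "relationship to the investigational drug, action taken, and outcomes". Severity appears once in that list and is tied to onset.

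Severity also appears in the 7.3 definitions: "Unexpected adverse drug experience is one not previously identified in nature, severity or frequency of incidence" in the Investigator brochure, the clinical plan or the IND. Section 7.3 then makes a drug-related event that is serious, unexpected or both reportable by the investigator to the IRB/EC.

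On the safety measure, 7.1 says "The principal measure of safety will be the incidence of adverse events reported during the study", together with a summary of the skin irritation scores. On analysis, 8.2.2 says "Adverse events, [REDACTED] will be summarized" and "Skin irritation tables will be produced at baseline collection and post-prep sample collection". The visible text of 8.2.2 does not mention severity.

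**The concern.** Severity of an adverse event is usually described by its worst grade. A grade fixed at onset can equal the worst grade or fall below it, but can never exceed it, so any error runs in one direction and makes events look milder than they were.

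Two uses of the grade are at stake. One is any later description of events by severity. The other is the judgement of whether a drug-related event is unexpected, because severity is one of the criteria. An event that was expected at its starting grade, but not at its peak, might not be recognisable as unexpected from the record alone. A peak grade that was not collected is also hard to reconstruct reliably at analysis.

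**Working it through.** The plan states no figure that depends on this field, so there is none to reproduce. The check is a reading of every visible section that deals with adverse events, severity or safety summaries.

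**1. Is a later grade requested anywhere?**
- 3.2 and 7.1 name incidence and irritation scores. They do not mention a severity grade.
- 7.3 Definitions use severity for expectedness and do not say which grade applies.
- 7.3 Recording and Reporting names severity at onset only.
- 8.2.2 says that events are summarised, with part of the sentence redacted.

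No visible section asks for maximum severity, a re-grade, or a new record when an event worsens.

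**2. Do other recorded items capture the worsening?**
- Seriousness covers death, threat to life, disability, hospitalisation and congenital anomaly. A reaction can go from mild to severe without meeting any of these.
- Action taken and outcomes may hint at worsening, but they are not grades.
- Skin irritation is rated before the baseline samples and before the post-prep samples (5.3.3.3, 7.2). Table 3.1A places the post-prep rating at 10 minutes. No later rating is visible, and 3.5 describes "a 1-day Screening Phase, and a 1-day Treatment Phase". For worsening after sampling, the adverse event record is the only visible instrument.

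**3. Direction.** Let s0 be the grade at onset and smax the highest grade reached. By definition smax ≥ s0, so s0 − smax ≤ 0 for every event. The error is zero for an event that does not worsen and negative for one that does.

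**4. Effect on incidence.** Incidence is the number of subjects with an event divided by the number of subjects. The grade enters neither, so the change is 0.

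**5. Scale, if a severity table were made.** Section 4 plans that "a total of 18 subjects are evaluable for efficacy at completion of the study". Assuming that 18 is also the safety denominator, one subject whose event worsened moves 1/18 = 5.6% of subjects from one severity row to another. The number treated may be larger: plates are incubated for 72 hours (6.2.1.1), so a Treatment Day baseline failure is known only after the product has been applied. If the six neutralisation subjects of 14.9.3 were also counted, which the plan does not say, the share would be 1/(18 + 6) = 1/24 = 4.2%. The plan gives no rate of events or of worsening, so the expected number of such subjects cannot be calculated.

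**The case against.** A reader might infer that worsening events will be reported as mild and that the adverse event table understates severity in the product's favour. The documents do not support that. No table by severity is visible, the sentence in 8.2.2 that might define one is partly redacted, and the field such a table would use is not stated. A reader might also infer that the principal safety measure is biased. It is not, because incidence does not depend on the grade.

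Other points on that side also have weight. The list in 7.3 is introduced by a word that leaves it open, and the Adverse Event Record itself is not shown, so the form may have room for a later grade. Redness in the first minutes is covered by the irritation scale, which has its own tables. The study is one 30-second application in healthy subjects, with product removed after the last sample and no visible follow-up visit, so onset and maximum severity will often coincide. On reporting, 7.3 already sends every drug-related event to the study monitor whatever its grade, and nothing stops an investigator from judging expectedness on the actual course.

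These points limit the size of the problem but do not remove it. An open list does not tell a site to record peak severity, whereas the text does tell it to record onset severity. The irritation scale visibly stops at post-prep sampling, and seriousness misses worsening that stays below its threshold.

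**Conclusion.** The point holds in a limited form. The only severity item named in 7.3 is the grade at onset, although the event is followed to resolution. A non-serious worsening need not be re-graded, any severity description using that field would be biased low, and the record may not show that peak severity was unexpected.

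The practical effect is probably small. Incidence does not change, few events are likely, and the 5.6% is an illustration of one hypothetical event in a table that may not exist. The conclusion rests on the visible text: the adverse event form is not shown, and parts of 5.3.3.3, 7.1 and 8.2.2 are redacted. If the form already collects maximum severity, what remains is to bring the wording of 7.3 into line with it.

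**What to change.** In 7.3 and on the Adverse Event Record, record maximum severity over the course of the event; onset severity may stay as an additional field. In 8.2.2, state that any summary by severity uses the maximum. The peak grade is then also on record when expectedness is judged.

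The cost is one extra form field and two sentences, with no added visit or procedure.

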## 8. STATISTICS

### 8.1 Data Sets Analyzed

Subjects with an average treatment day baseline of  $\geq 3.0 \log_{10}$  CFU/cm^2 at each of the sampling sites (center, mid-peripheral and peripheral) within the test site (back region) will be included in the analysis.

[REDACTED]

## 8.2 Statistical Methods

- CFU/ml will be converted to CFU/cm^2.
- Summary tables will be produced for all responses. Summary tables for log10 recovery, log10 baseline and log10 reduction from baseline will include n, mean, standard deviation, median, minimum and maximum.

### 8.2.1 Efficacy Analyses

A mean log10 reduction of 2.0 in all 3 sampling locations is needed to support the proposed coverage area.

### 8.2.2 Safety Analyses

Adverse events, [REDACTED] will be summarized.

Skin irritation tables will be produced at baseline collection and post-prep sample collection.

## 8.3 Sample Size Justification

[REDACTED] The rationale for the number of subjects is based on EN test methods EN1499, EN1500 and EN12791 which require between 12 and 18 subjects.

## 8.4 Criteria for Termination of the Study

3M reserves the right to terminate the study at any time for business reasons.

## 8.5 Procedures for Accounting for Missing, Unused, and Spurious Data

Any non-use of data will be discussed and justified in the blinded review of data at the data lock meeting and documented in the meeting minutes.

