### 3.1 Study Type and Methodology

This is a prospective, randomized, uncontrolled single-center study in healthy subjects.

This study will be conducted using a modification of ASTM E1173-15 Standard Test Method for Evaluation of Preoperative, Precatheterization, or Preinjection Skin Preparations. The 2-log10 reduction criteria (dry site) will be used to evaluate efficacy. Time points for sample collection are baseline (pre-prep) and 10 minutes or 13 minutes (post-prep).

Table 3.1A provides a summary of the study procedures. A schematic diagram of the study is included in Appendix 14.1.

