### 3.2 Primary and Secondary Endpoints

#### Primary Endpoint:

The primary endpoint, coverage area with efficacy, is measured by  $\log_{10}$  reductions calculated by subtracting the  $\log_{10}$  number of microorganisms recovered at a specified sampling time following product application from the  $\log_{10}$  number of microorganisms recovered from the baseline sampling. Baseline samples must satisfy the inclusion criteria to be used in data analysis,  $\geq 3.0$   $\log_{10}$  CFU/cm^2 in all three sampling sites on the treatment site. The sampling time for efficacy evaluation will be specified per the randomization schedule as 10 minutes or 13 minutes post-product application.

[REDACTED]

[REDACTED]

[REDACTED]

The principal measure of safety will be the incidence of adverse events reported during the study and a summary of the skin irritation rating scores.

[REDACTED]

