### 3.3 Randomization

The three post-product application sampling sites will be randomized so that 2 of the 3 sites will be sampled at one of the post-product application sample times (10 minutes or 13 minutes) and the third sampling is collected at the remaining sample time.

The randomization schedule will be provided to the study site in a separate document.

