### 6. ASSESSMENT OF EFFICACY

#### 6.1 Efficacy Parameters

The primary measure of coverage area with efficacy [REDACTED] is measured as  $\geq 2 \log_{10}$  CFU/cm^2 reductions calculated by subtracting the  $\log_{10}$  number of microorganisms recovered at a specified sampling time following product application from the  $\log_{10}$  number of microorganisms recovered from baseline sampling. Baseline samples must satisfy the inclusion criteria,  $\geq 3.0 \log_{10}$  CFU/cm^2 in each of the 3 sampling sites, to be used in data analysis.

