### **12.3 Completion and Return of Case Report Forms**

Electronic data capture (eDC) software will be used for this study. Data may be recorded onto data collections sheets prior to data entry or may be entered directly into the eDC system. Microbiological count data will be recorded onto DCSs prior to entry into the eDC system. If a correction is required, a single line must be drawn through the error. The person making the correction will initial, date, and provide a reason for the error (if not self-evident). Once the forms are completed, the monitor will review the case report form (CRF) to assure accuracy and completeness.

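### Does the blinded review in section 8.5 leave room for outcome-aware exclusions, given that this one-product study has no treatment code to mask?

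*Combined protocol and SAP*

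**What the plan says.** On discretionary exclusions, section 8.5 is a single sentence: "Any non-use of data will be discussed and justified in the blinded review of data at the data lock meeting", with the outcome recorded in the meeting minutes. Section 8.6 adds that departures from the statistical plan are documented in the study report.

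On design, section 3.1 states "This is a prospective, randomized, uncontrolled single-center study in healthy subjects". The only randomized item visible is the sampling time. Section 3.3 begins "The three post-product application sampling sites will be randomized so that 2 of the 3 sites will be sampled at one of the" and goes on to name the two times, 10 and 13 minutes.

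On data flow, section 12.3 has microbiological counts written on data collection sheets and then entered electronically, after which "the monitor will review the case report form (CRF) to assure accuracy and completeness". Section 9 gives the sponsor's monitor direct access to source documents.

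On the success rule, section 8.2.1 says that a mean log10 "reduction of 2.0 in all 3 sampling locations is needed to support the proposed coverage area". Sections 2 and 4 aim for 18 evaluable subjects.

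On the fixed baseline rule, section 3.2 says "Baseline samples must satisfy the inclusion criteria to be used in data analysis", with a threshold of 3.0 log10 CFU/cm² at all three sites. Section 6.1 repeats the threshold "in each of the 3 sampling sites, to be used in data analysis", and section 8.1 says that subjects who reach it "at each of the sampling sites (center, mid-peripheral and peripheral) within the test site (back region) will be included in the analysis". Redacted text follows in section 8.1.

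**The concern.** In a controlled trial, a blinded data review means that the reviewers do not know who received what. Here everyone receives the same product. Masking the 10- or 13-minute schedule would leave every baseline count, post-prep count and log10 reduction readable. If that were all the word covered, the meeting could decide which subjects to leave out while seeing which ones pull a location mean below 2.0. The visible success rule compares three means with 2.0 and uses no confidence bound, so a single exclusion can decide a close result.

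A second feature points the same way. Product is applied straight after baseline sampling (section 5.3.3.2) and plates incubate for 72 hours (section 6.2.1.1). The treatment-day baseline rule can therefore remove only subjects who have already been treated. The filtered count is also the first term of the log10 reduction. Subjects kept because their baseline count happened to read high also have their reduction read high, which is regression to the mean in the product's favour.

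**Working it through.** **The plan's own figure.** The 18 evaluable subjects cannot be reproduced by formula. Section 8.3 takes the number from EN methods that ask for 12 to 18 subjects, and the visible text gives no SD, effect size or power. Every SD, correlation and flora mean below is therefore an assumption.

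**1. What one exclusion can do.** Take 19 subjects with location mean m and drop one with reduction d. The new mean is (19m − d)/18, and it reaches 2.0 when d ≤ 19m − 36.
- m = 1.98: d ≤ 37.62 − 36 = 1.62
- m = 1.95: d ≤ 37.05 − 36 = 1.05
- m = 1.90: d ≤ 36.10 − 36 = 0.10

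An ordinary low value is enough at 1.98. At 1.90 the subject must show almost no reduction.

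**2. Worst-case exclusion.** This simulation compares 18 subjects with no exclusion against 19 with the lowest subject mean removed. It gives the probability that all three means reach 2.0, at between-location correlation 0 / 0.3 / 0.6.

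| True mean | SD | No exclusion | Lowest of 19 dropped |
|---|---|---|---|
| 1.9 | 0.5 | 0.01 / 0.03 / 0.06 | 0.02 / 0.06 / 0.13 |
| 1.9 | 1.0 | 0.04 / 0.08 / 0.14 | 0.08 / 0.16 / 0.26 |
| 2.5 | 0.5 | 1.00 throughout | 1.00 throughout |
| 2.5 | 1.0 | 0.95 to 0.96 | 0.98 |

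At true mean 1.8 the probability stays at or below 0.13 even with the exclusion. The average rise per location mean is 0.03 to 0.04 at SD 0.5 and 0.06 to 0.09 at SD 1.0. With the true mean at exactly 2.0, SD 0.8 and correlation 0.3, dropping the lowest one or two of 18 raises the probability from 0.20 to 0.32 or 0.44. A product with true means of 2.0 does, however, meet the stated criterion.

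**3. Baseline rule.** Let a subject's flora be f ~ N(m, s_b), let count error have SD s_w, and let P = Φ((f − 3)/s_w). A subject must pass three screening counts and three treatment-day counts, with independent errors. If post-prep counts follow true baseline one for one:
- shift in the mean = E[P³ · s_w · φ((3 − f)/s_w) · P²] / E[P⁶]
- share of treated subjects failing = 1 − E[P⁶]/E[P³]

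Results for s_b 0.4 to 0.6 and s_w 0.2 to 0.5:
- m = 4.0: shift +0.001 to +0.032, with 1% to 11% failing.
- m = 3.0 to 3.6: shift +0.005 to +0.144, with 6% to 52% failing. The top value (m = 3.0, s_b = 0.4, s_w = 0.5) needs about half of treated subjects to fail.
- s_w = 0.2: shift at most +0.019.

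If post-prep counts do not depend on baseline at all, simulation gives shifts up to about +0.28. Part of that is a real difference between the subjects kept and those removed. The direction is upward throughout, but the size depends on inputs that the documents do not give.

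**4. Would an all-treated table be closer to the truth?** This uses mean flora 3.0, s_b 0.5 and s_w 0.4. The recovery floor is the lowest count that can be recorded.

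| True reduction | Floor (log10) | Evaluable mean (error) | All-treated mean (error) |
|---|---|---|---|
| 2.0 | none | 2.07 (+0.07) | 2.00 (0.00) |
| 2.0 | 1.0 | 2.05 (+0.05) | 1.96 (−0.04) |
| 2.5 | 1.0 | 2.44 (−0.06) | 2.30 (−0.20) |

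The all-treated set is better in the first row and about equal in the second. In the third it is clearly worse. The actual floor is not visible, so neither set can be called the reference.

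**The case for a change.** The strongest argument for a change is that section 8.5 carries no redaction mark, names no exclusion criteria and leaves its one safeguard undefined. Only masking of post-prep counts would protect the result, and one sentence would say so at almost no cost. Counts exist in the database before lock and the monitor can see them. Near 2.0 the calculation shows that one outcome-aware exclusion can roughly double a small chance of passing. On the baseline rule, the upward direction is not in doubt, and a supportive table would use data already collected.

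Part of this stands. The term is undefined, and a sponsor that wrote down what is masked would lose nothing. The upward direction of the baseline shift also stands, and the visible text does not support calling it slight.

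The rest is weaker. Review of forms for accuracy and completeness does not make the monitor a decision-maker on exclusions. The worst case assumes that reviewers see the reductions and drop the least favourable subject, then justify that in minutes under a plan that calls the review blinded. If the review is already masked to outcomes, the added sentence would only record existing practice. The baseline rule involves no discretion at the lock meeting, so section 8.5 does not govern it. Its purpose is plain: a 2-log10 drop cannot be shown without enough starting flora. Redacted text after section 8.1 may also define further analysis sets.

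**Conclusion.** No change is called for. On the first point the plan leaves a detail unstated that a competent team fills sensibly. In a study with one product, a blinded review has a useful meaning only if outcomes are withheld, and the plan already requires justification and minutes. Section 8.2 also reports n, minimum and maximum, so missing subjects would show in the tables. The harm needs conduct that the documents do not describe, together with a location mean close to 2.0. Under the assumed worst case at true mean 1.9, the probability of passing rises by at most about 0.12 (0.14 to 0.26, at SD 1.0 and correlation 0.6). At true mean 2.5 it is unchanged at SD 0.5 and rises by 0.02 to 0.03 at SD 1.0.

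On the second point the plan makes a fair trade-off. The baseline rule is objective, fixed in advance and stated consistently in sections 3.2, 6.1 and 8.1. It is expected to raise the evaluable means, by about +0.001 to +0.144 if post-prep counts follow baseline and by up to about +0.28 if they do not. An all-treated table would change no success criterion and, depending on the unknown recovery floor, could be further from the truth (2.30 against 2.44 for a true 2.5). It offers no clear gain.

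These sizes rest on assumed flora means, SDs, correlations and floors. Persistent differences between sampling positions were not modelled, because the site diagram is not visible.
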